#### 7.1.2 **Microbiologic Response**

Per-pathogen and per-subject microbiologic response will be programmatically determined at the EOT and PTE Visits in the micro-ITT and ME populations (by definition subjects in the ME population cannot have an indeterminate response).

Microbiological response will be derived using electronically transferred microbiology data from the central laboratory (or local laboratory if central data are not available).

Overall per-pathogen microbiological response at PTE is determined as follows (Table 7) from the per-pathogen microbiological responses at the EOT and PTE Visits.

#### 7.1.2.1 **Pathogen Determination**

A pathogen is defined as bacteria implicated as causative in a subject's AP. Baseline pathogens and post-baseline pathogens will be identified for each patient programmatically with manual review and confirmation. Sponsor determination review will be performed in a blinded manner by Sponsor's internal microbiology review committee. Details are documented in the Pathogen and  $CE^2$ .

Status: Approved Approved Date: Version: 1.0 PTK0796-AP-17202 Statistical Analysis Plan

Omadacycline (PTK 0796)

Paratek Pharma, LLC

PTK0796-AP-17202 Statistical Analysis Plan

#### 7.1.2.2 **Microbiologic Response**

Per-pathogen microbiological response will be programmatically determined at the EOT and PTE Visits in the micro-ITT and ME populations (subjects in the ME population cannot have an indeterminate response).

Pathogen microbiological outcome categories are: eradication, persistence, and indeterminate and these are defined in the following table (Table 7).

Category	Criteria			
Eradication	The demonstration that the baseline bacterial pathogen is reduced to $< 10^4$ CFU/mL on urine culture and negative on repeat blood culture (if positive at baseline)			
Persistence	The urine culture taken at the study visit grows $\geq 10^4$ CFU/mL of the baseline pathogen identified at study entry and/or a positive blood culture at the study visit demonstrates the same baseline pathogen. Pathogens that demonstrate persistence at EOT will be considered as persistence at PTE.			
Indeterminate	No follow-up urine culture is available, or the follow-up urine culture cannot be interpreted for any reason. For a baseline blood pathogen, no follow-up blood culture is available.			

Table 7 Per-Pathogen Microbiologic Response at EOT and PTE

CFU = colony forming units, EOT = end of treatment, PTE = post therapy evaluation.

Per-subject microbiological responses will be based on per-pathogen outcomes (see Table 8). An overall per-subject microbiologic response at EOT and PTE will be programmatically determined for each subject based on the individual outcomes for each baseline pathogen. For a subject to have a microbiologic response of success, the outcome for each baseline pathogen must be eradicated. If the outcome for any pathogen is persistence, the subject will be considered to have a microbiologic response of failure. A persistent baseline pathogen at EOT will be considered persistence at PTE.

Table 8	Per-Subject Microbiologic Response at EOT and PTE
---------	---

Category	Criteria
Success	The outcome of all baseline pathogens must be eradication at the specified visit (EOT or PTE)
Failure	The outcome of at least 1 baseline pathogen is persistence. Subjects with a persistence determination at EOT will be considered to have persistence at PTE.
Indeterminate	The outcome of at least 1 baseline pathogen is indeterminate and there is no outcome of persistence for any baseline pathogen

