### **7.14 Permitted Treatments**

All other treatments not specified as prohibited are permitted during the study. Subjects requiring additional or alternative antibacterial therapy for their AP will be judged as Clinical Failures and test article will be discontinued. Further treatment for their infection is at the discretion of the investigator or the subject's health care provider and will be considered as a concomitant medication.

Subjects should be encouraged to contact site personnel before starting any new treatment.

For all treatments received by the subject during the study, relevant information must be recorded on the subject's eCRF.

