## 8.9 Microbiologic Response

Microbiologic outcome at EOT and PTE will be programmatically determined for each pathogen isolated at baseline. Per-pathogen microbiologic response categories are eradication, persistence and indeterminate.

Category	Criteria
Eradication	The demonstration that the baseline bacterial pathogen is reduced to $< 10^4$ CFU/mL on urine culture and negative on repeat blood culture (if positive at baseline)
Persistence	The urine culture taken at the study visit grows $\geq 10^4$ CFU/mL of the baseline pathogen identified at study entry and/or a positive blood culture at the study visit demonstrates the same baseline pathogen. Pathogens that are a persistence at EOT will be considered a persistence at PTE.
Indeterminate	No follow-up urine culture is available, or the follow-up urine culture cannot be interpreted for any reason. For a baseline blood pathogen, no follow-up blood culture is available.

CFU = colony forming units, EOT = end of treatment, PTE = post therapy evaluation.

An overall per-subject microbiologic response at EOT and PTE will be programmatically determined for each subject based on the individual outcomes for each baseline pathogen. For a subject to have a microbiologic response of success, the outcome for each baseline pathogen must be eradicated. If the outcome for any pathogen is persistence, the subject will be considered to have a microbiologic response of failure. Subjects with a persistence at EOT will be considered a persistence at PTE.

Category	Criteria
Success	The outcome of all baseline pathogens must be eradication at the specified visit (EOT or PTE)
Failure	The outcome of at least 1 baseline pathogen is persistence. Subjects with a persistence at EOT will be considered a persistence at PTE.
Indeterminate	The outcome of at least 1 baseline pathogen is indeterminate and there is no outcome of persistence for any baseline pathogen

EOT = end of treatment, PTE = post therapy evaluation.

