#### b. Concomitant Antibiotic Therapy

Subjects who receive any systemic concomitant antibiotic therapy from the start of administration of the first dose of test article through the EOT visit (CE-EOT population), PTE visit (CE-PTE population) or FFU visit (CE-FFU population) that is potentially effective against the baseline pathogen, will be excluded from the CE population. If no pathogen is isolated and the systemic concomitant antibiotic is effective against Gram-negative uropathogens, the subject will be excluded from the respective CE population. Subjects who are a clinical failure on the particular visit and received non-study antibiotics for insufficient therapeutic effect of the test article, will not be excluded from the CE populations. Subjects who receive a systemic concomitant antibiotic that is not potentially effective against the baseline pathogen will be included in the CE populations.

c. Evaluable Success and Failure

Evaluable success: The subject received at least 3 doses of active test article and the investigator classifies the subject as a clinical success at the EOT visit (CE EOT population) or the overall clinical response (based on the investigator's assessment) at the PTE visit (CE-PTE population) or the overall clinical response (based on the investigator's assessment) at the FFU visit (CE-FFU population) is clinical success/cure.

Evaluable failure: The subject received at least 2 doses of active test article and the investigator classifies the subject as a clinical failure at the EOT visit (CE EOT population) or the overall clinical response (based on the investigator's assessment) at the PTE Visit (CE-PTE population) or the overall clinical response (based on the investigator's assessment) at the FFU visit (CE-FFU population) is clinical failure/relapse.

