#### 4.5 Microbiologically Evaluable Populations

The microbiologically evaluable (ME) population will include subjects in the CE and micro-ITT populations who have both an appropriately collected post-baseline urine sample and an interpretable post-baseline urine sample. An interpretable post-baseline urine culture is one that has a clearly identified pathogen or one where the baseline pathogen(s) can be excluded (ie, there is no growth of the baseline pathogen).

Since patient count may differ depending on timepoint, ME populations will be defined by milestone visit (ME-EOT and ME-PTE).

93 Version: 1.0 Status: Approved Approved Date: PTK0796-AP-17202 Statistical Analysis Plan

Omadacycline (PTK 0796)

Paratek Pharma, LLC

PTK0796-AP-17202 Statistical Analysis Plan

The ME populations consist of subjects in the micro-ITT population and the CE-EOT and CE-PTE populations, respectively who also have:

- A clean-catch urine specimen at the EOT and PTE visits, and
- Interpretable urine culture results at the EOT and PTE visits.

Subjects with an unfavorable microbiological outcome at EOT will be included in the ME-PTE population, regardless of whether they provide a urine culture at the PTE visit.

An interpretable post-baseline urine culture is one that has a clearly identified pathogen or one where the baseline pathogen(s) can be excluded (i.e., there is no growth of the baseline pathogen). A urine culture is considered uninterpretable if more than two bacterial isolates are identified, unless any of the following is observed:

- There is  $<10^4$  CFU/mL of the baseline pathogen(s), indicating eradication.
- There is  $\geq 10^4$  CFU/mL of the baseline pathogen(s), indicating persistence

At any visit after Screening, a pathogen the same species as the Baseline pathogen with a CFU count of  $\ge 1 \times 10^4$  CFU/mL should be considered a persisting pathogen.

At any visit after Screening, any culture with a CFU count of  $< 10^4$  CFU/mL should be considered a negative culture.

PTK0796-AP-17202 Statistical Analysis Plan

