- Prior and Concomitant Medication start date imputation will be imputed according to table in Appendix 4 Concomitant Medication Start Date Imputation.
- 2. Efficacy Data
- Analysis of efficacy data will be based on the available data, unless otherwise stated.
- Missing data for clinical and microbiological outcomes is denoted "indeterminate", unless any of the below rules apply.
- Missing microbiological outcomes at EOT will be imputed by last day of test article intake.
- The Overall Clinical Response at PTE and FFU visits are derived based on the "worst case scenario" to accommodate for missing visit assessments and intercurrent events (eg rescue

93 Version: 1.0 Status: Approved Approved Date: PTK0796-AP-17202 Statistical Analysis Plan

Omadacycline (PTK 0796)

Paratek Pharma, LLC

PTK0796-AP-17202 Statistical Analysis Plan

medication at EOT visit). Similar imputations were applied to microbiological response endpoints. Details are described in Section 7.

• mPSAQ data for bothersome score will be imputed with score of 0 for each question for which severity is answered "Did not have".

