## 8.2 Duration of Exposure to Test Article and Compliance

Exposure summary by treatment group and separately by route of administration (iv, po) will be presented for the Safety and micro-ITT populations.

The distribution of subjects by the total number of days on therapy (0, 1, 2-3, 4-6, 7-10, 11-14, and > 14 days), the number of days on iv infusion and the number of days of oral test article will be presented.

A summary of the number of days of iv therapy prior to oral switch defined as 24-hour periods (ie, time to oral switch), the day of oral switch, and the criteria for iv to oral switch will be presented by treatment group. For the Safety population, the summary of test article exposure will be based on the actual treatment received whereas for all other analysis sets, the summary will be based on the randomized treatment.

Treatment compliance is defined as the number of iv doses (including partial doses, active and placebo) and oral

% Compliance =  $100\% * \frac{number of doses actually received}{number of doses expected to received}$ 

The number of dosed expected to be received by the patient will be calculated over the time period defined by the first infusion date and the last dose date.

All oral doses should be taken in a fasted state. Fasting is defined as no food, antacids or multivitamins containing multivalent cations (eg, aluminum, magnesium, calcium, bismuth, iron, or zinc) or drink except water for at least 6 hours before dosing. After dosing, no food is permitted for 2 hours as well as no dairy products, antacids or multivitamins containing multivalent cations (eg, aluminum, magnesium, calcium, bismuth, iron, or zinc) for 4 hours.

Number of subjects and percentage with a compliance  $\geq 80\%$  will be presented. A summary of compliance to oral test article intake with the pre and post-dose fasting requirements will also be provided for subjects switching to oral administration. The percent fasting compliance will be determined based on the total doses taken for days the subjects were on po medication. The percentage of subjects who were < 50\%, 50% to < 80%, and 80% to 100% compliance with the pre-dose and post-dose fasting requirements met will be summarized.

Omadacycline (PTK 0796)

PTK0796-AP-17202 Statistical Analysis Plan

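### As visible, a urine culture taken after rescue antibacterials can still score as eradication; a narrow set of rescued subjects is misclassified in the stand-alone microbiologic results.

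*SAP*

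**What the plan says.** **Scoring.** SAP Table 7 calls a baseline pathogen eradicated when the urine count falls below 10^4 CFU/mL and, if blood was positive at baseline, the repeat blood culture is negative. Table 8 gives per-subject Success when every baseline pathogen is eradicated at the visit. The carry-forward is: "Pathogens that demonstrate persistence at EOT will be considered as persistence at PTE". Protocol 8.9 matches: "Pathogens that are a persistence at EOT will be considered a persistence at PTE". SAP 4.5 adds that any post-Screening culture below 10^4 CFU/mL "should be considered a negative culture".

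**Rescue.** Protocol 7.14 states: "Subjects requiring additional or alternative antibacterial therapy for their AP will be judged as Clinical Failures and test article will be discontinued". Protocol 8.19 still asks subjects who stop treatment early to attend EOT and PTE where possible, so a post-rescue PTE culture can exist.

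**Evaluable populations.** Under SAP 4.4, item 3b, clinical failures who "received non-study antibiotics for insufficient therapeutic effect of the test article, will not be excluded from the CE populations". Item 3c accepts a failure if "The subject received at least 2 doses of active test article". Expected doses for compliance (SAP 8.2) are "calculated over the time period defined by the first infusion date and the last dose date", so stopping early does not itself make a subject non-compliant.

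**What is promised.** SAP 5.3 describes worst-case derivation of clinical response, gives rescue medication as its example of an intercurrent event, and continues: "Similar imputations were applied to microbiological response endpoints. Details are described in Section 7". It also says that a missing EOT microbiologic outcome is imputed from the last day of test article. SAP 7.2.2.1 lists presumed persistence among the unfavorable outcomes. Table 7 does not define it.

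**The concern.** A culture taken after a second effective antibacterial was started reflects both drugs. If it is read as eradication, clearance by the rescue drug may be credited to the test article. The error can only add successes, and it adds more in an arm with more rescue, so it would tend to flatter a weaker regimen.

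There is also an oddity within the endpoint. SAP 7.2.2.1 counts Indeterminate as unfavorable. A subject with no usable PTE culture therefore counts against her arm, while a documented Clinical Failure whose urine cleared after rescue counts in its favor.

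The stake is modest but real. SAP Table 12 says the efficacy endpoints are meant to inform dose selection for a possible Phase 3 program, and Protocol 12.6.2 plans eradication by pathogen and by pathogen and MIC, where cells will be small.

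**Working it through.** **Step 1: the rule as a truth table.** Take one urine pathogen and no baseline bacteremia. Let E = eradication, P = persistence, I = indeterminate. Tables 7 and 8 give this per-subject response at PTE:

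| EOT | PTE = E | PTE = P | PTE = I |
|---|---|---|---|
| E | Success | Failure | Indeterminate |
| P | Failure | Failure | Failure |
| I | Success | Failure | Indeterminate |

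Two of the nine cells give Success: E/E and I/E. Rescue status is an input to neither. A bacteremic subject also needs a negative repeat blood culture, and rescue does not enter there either.

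**Step 2: which rescued subjects reach those cells wrongly.**

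- *Rescue during treatment, EOT urine at or above 10^4 CFU/mL before rescue.* EOT is P, so PTE is Failure whatever the rescue drug does. Correct.
- *Rescue during treatment, EOT urine below 10^4 before rescue.* The test article had already cleared the urine. Success at EOT is correct. The PTE culture then says little about durability, but the clearance was not the rescue drug's.
- *EOT culture missing.* SAP 5.3 substitutes the last day of test article. Urine is cultured daily from Day 2 (Protocol 9.2.2 to 9.2.10), so a result under test article will usually exist.
- *Clear at EOT, relapse, rescue, PTE urine below 10^4.* E/E, so Success. The definition of Clinical Failure at PTE (SAP 7.1.1.2) includes reappearance of symptoms that needs further therapy. No urine culture is scheduled between EOT and PTE to show regrowth. Misclassified if the pathogen had regrown.
- *Rescue begun before the EOT sample.* EOT may fall up to 2 days after the last dose, so both cultures can follow rescue. E/E, so Success. Not attributable to test article.
- *EOT stays indeterminate after the 5.3 rule.* I/E, so Success on the strength of a post-rescue culture alone.

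The last three are the gap.

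**Step 3: populations.** All three paths can occur in micro-ITT. The first two can also reach ME-PTE, because items 3b and 3c of SAP 4.4 and the compliance definition keep the subject in, provided her cultures are interpretable and she meets the other CE criteria.

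**Step 4: size.** The plan has no figure for this issue and no rescue rate. The planning size of 30 per group (SAP 3.1) serves only as a scale.

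- Shift per case = k/30: 1/30 = 3.3 points, 2/30 = 6.7, 3/30 = 10.0.
- Exact (Clopper-Pearson) 95% limits, with B(q; a, b) the beta quantile: lower B(0.025; x, n−x+1), upper B(0.975; x+1, n−x). For 21/30 (70.0%): 50.6 to 85.3%. For 22/30 (73.3%): 54.1 to 87.7%. One case is small against sampling error.
- In a pathogen-by-MIC cell of 10 isolates (assumed size), one case moves eradication by 1/10 = 10 points.
- If the same share of both arms is misclassified, both rates rise equally and the difference between arms is unchanged.

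**Step 5: with the rule proposed below.** For rescued subjects, E/E and I/E become Failure when the PTE culture follows rescue for the index infection. The composite does not change, because Protocol 12.5.1 already makes a Clinical Failure an overall Failure.

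**The case against.** The strongest reply is that the EOT culture already does this work. Rescue stops test article, stopping triggers EOT, and Protocol 9.3 asks for the EOT procedures on that day for a discontinued subject. That culture normally shows the urine under test article as rescue begins. Persistence there is locked in, and clearance there belongs to the test article. This stands, and it rules out a tempting stronger reading: that every rescued subject with clean PTE urine is a false success. For the same reason I give no range built from an assumed rescue share times an assumed clearance share. It would count subjects already clear before rescue, and both inputs would be invented.

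A reader might also infer that SAP 5.3 is flatly contradicted. The documents do not support that. Table 5 has no separate rescue input either. It carries EOT failure to PTE, and carrying EOT persistence to PTE is the direct parallel. The commitment is partly met. What it lacks is a microbiologic rule for the intercurrent event that 5.3 names.

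Nor can one say that the plan has no rescue rule. In the copy available, SAP 7.1.2.3, 7.1.3, 7.2.2.2, 7.2.2.3, 7.2.3 and the content of 7.2.4 have no body text, and the Pathogen and CE Review Plan is a separate document. The use of presumed persistence hints that further categories exist somewhere.

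Finally, microbiologic response is a culture-based endpoint meant to support the clinical one, and the concordance table in SAP 7.2.2.1 will show Clinical Failures with microbiologic success. That cell caps the problem. As described, though, it does not separate cultures taken before rescue from those taken after, and it is not by pathogen or MIC.

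**Conclusion.** The point holds in a narrow form. On the visible text, post-rescue cultures can count as Eradication and Success, and three paths lead there: relapse after EOT with rescue before PTE, rescue begun before the EOT sample, and an EOT result that stays indeterminate. The SAP 5.3 commitment is met only in part, and presumed persistence has no visible definition.

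Only stand-alone per-subject and per-pathogen microbiologic response in micro-ITT and ME is touched. A reader might infer that the composite or clinical results are inflated. They are not, since rescue for the index infection already makes the subject a Clinical Failure. All efficacy endpoints are exploratory under SAP 7.1.

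The size is 3.3 points per case at 30 per arm, with the number of cases unknown. The conclusion assumes that no rescue rule sits in the unavailable SAP text or in the Review Plan. Confidence is medium for that reason. This is worth fixing, but it does not threaten the trial's main reading.

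**What to change.** If a rescue rule already exists in the SAP text not available here or in the Pathogen and CE Review Plan, cite it in Tables 7 and 8. If not, add one:

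- A culture taken after a potentially effective non-study systemic antibacterial was started cannot count as Eradication.
- If that drug was given for insufficient effect or relapse of the index infection, score the culture presumed persistence (per-subject Failure), and define this category in Table 7.
- If it was given for another reason, score Indeterminate. This fits SAP 4.4, item 3b, which already removes such subjects from CE.
- Cultures taken before rescue, including the EOT culture, stand as read for their own visit.
- Report the culture-only result as a sensitivity analysis.

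The cost is one derivation and one extra table. Antibacterial dates and reasons for therapy are already recorded on the eCRF (Protocol 7.12 and 8.18). The downside is that a pathogen truly eradicated by test article before rescue is not credited at PTE in the main table, and microbiologic response then overlaps more with clinical failure. The culture-only table keeps that information.

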#### Main Criteria for Exclusion:

1. Pregnant or nursing (breastfeeding) women.
2. Receipt of any dose of a potentially therapeutic antibacterial agent (with potential activity against uropathogens in the urinary tract) from 72 hours prior to randomization until the first dose of test article. [NOTE: Subjects who developed the current pyelonephritis while receiving prophylactic antibacterial therapy (for any reason) may be eligible if all prophylactic antibacterials are stopped (no further dosing after randomization) and approved by the study medical monitor.]
3. Anticipated need for systemic antibacterial therapy other than test article (for treatment or prophylaxis) during the study period.
4. Infection at baseline that in the Investigator's judgment would require more than 10 days of antibacterial therapy (subjects determined to have bacteremia based on blood cultures collected at screening can be treated for up to 14 days).
5. Symptoms of AP present longer than 7 days prior to randomization.
6. Confirmed or suspected AP caused by a pathogen that is resistant to tetracyclines or fluoroquinolones, including infection caused by fungi (eg, *Candida* spp.) or mycobacteria (eg, urogenital tuberculosis).
7. Known or suspected rapidly-progressing or life-threatening illness including septic shock. Septic shock can be identified using the clinical criteria of hypotension requiring vasopressor therapy to maintain mean arterial blood pressure of 65mmHg or greater and having a serum lactate level greater than 2 mmol/L after adequate fluid resuscitation.
8. Use of an indwelling urinary catheter, nephrostomy tubes or other indwelling urinary tract device within the 30 days prior to randomization.
9. Confirmed or suspected urinary retention ( $\geq 100$  mL of residual urine after voiding) from any cause, including neurogenic bladder or obstruction.
10. History of surgically modified or abnormal urinary tract anatomy (eg, bladder diverticula or redundant urine collection system).
11. Confirmed or suspected complete or partial obstruction of the urinary tract, or obstructive uropathy that is scheduled to be medically or surgically relieved during the study therapy period (eg, renal calculi, urethral or ureteral stricture).
12. Confirmed or suspected renal disease or condition that, in the opinion of the investigator, may confound the assessment of efficacy, including but not limited to the following:
  - Perinephric or intrarenal abscess

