## 7.13 Prohibited Therapy

- All investigational medications or devices used during the 30 days prior to Screening are prohibited.

All of the following therapies are excluded starting from the time of consent through EOT visit:

- Potentially therapeutic antibacterial agents (with potential activity against uropathogens responsible for AP) are prohibited for 72 hours prior to randomization through EOT, with

the exception of cases where a subject is deemed a clinical failure during the course of the study and requires treatment with an additional antibacterial agent

- Subjects will be instructed to avoid taking antacids and multivitamins containing multivalent cations (eg, aluminum, magnesium, calcium, bismuth, iron, or zinc) for 6 hours before and within 4 hours after oral doses

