#### **8.8.1.2 Investigator's Assessment of Clinical Response at PTE**

For subjects who were determined to be a clinical success or indeterminate at the EOT visit, the investigator will determine whether or not the subject meets the criteria of 1 of the following clinical outcomes:

- **Clinical Success:** The complete resolution or significant improvement of the baseline signs and symptoms of AP symptoms at the PTE such that no additional antimicrobial therapy is required for the current infection.
- **Clinical Failure:** No apparent response to therapy or persistence of signs and symptoms of infection or reappearance of signs and symptoms at or before the PTE visit such that use of additional systemic antimicrobial therapy for the current infection is required or death at or before the PTE visit.
- **Indeterminate:** PTE visit not completed.

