# 7.2.2 Microbiological Response Analysis

# 7.2.2.1 Per-Subject Microbiological Analysis

The per-subject microbiological (overall) response at the EOT and PTE Visits in the micro-ITT, ME-EOT and ME-PTE populations will be determined to support the clinical findings.

The number and percentage of subjects classified with a favorable (eradication and presumed eradication) and unfavorable (persistence, presumed persistence, and indeterminate) microbiological response (by definition, indeterminates are excluded from the ME population) will be tabulated for both treatment groups. Exact 95% CIs will be determined for the point estimates of the favorable microbiologic outcome rates in each treatment group.

Concordance of microbiological outcome with clinical outcome at EOT and PTE visits for micro-ITT and ME populations will be provided.

Number: GEN-STP-0293 Version: 1.0 Status: Approved Date: PTK0796-AP-17202 Statistical Analysis Plan

Omadacycline (PTK 0796)

Paratek Pharma, LLC

PTK0796-AP-17202 Statistical Analysis Plan

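### PTE microbiologic response ignores rescue antibacterials given after a negative EOT culture, so eradication achieved with rescue counts as microbiologic success

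*SAP*

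**What the plan says.** - **Microbiologic rule.** In SAP 7.1.2.2 (Table 7), eradication is "The demonstration that the baseline bacterial pathogen is reduced to" below 10^4 CFU/mL in urine, plus a negative repeat blood culture if blood was positive at baseline. Table 8 calls the subject a success when every baseline pathogen is eradicated at the visit. The one link between visits is "A persistent baseline pathogen at EOT will be considered persistence at PTE". Protocol 8.9 has the same rule. Neither mentions non-study antibacterials.
- **Stated intent.** SAP 5.3 derives clinical response on a worst-case basis to allow for missed visits and intercurrent events, with rescue medication as its example. It says similar imputations apply to microbiologic endpoints and refers to Section 7 for details.
- **Populations.** SAP 4.4 (item 3b) removes from CE-PTE subjects given another potentially effective systemic antibiotic before PTE. It keeps "Subjects who are a clinical failure on the particular visit and received non-study antibiotics for insufficient therapeutic effect of the test article". ME-PTE is built from CE-PTE and micro-ITT. Micro-ITT has no antibacterial exclusion, and SAP 5.4 uses EOT and PTE data whenever collected.
- **Clinical and composite rules.** Protocol 7.14 makes rescue for pyelonephritis a clinical failure. Protocol 8.8.1.2 defines PTE failure by signs and symptoms "such that use of additional systemic antimicrobial therapy for the current infection is required". Under protocol 12.5.1, either a clinical or a microbiologic failure makes the composite a failure.
- **Analysis.** SAP 7.2.2.1 tabulates favorable and "unfavorable (persistence, presumed persistence, and indeterminate) microbiological response" with exact intervals per arm, plus concordance with clinical outcome. Protocol 12.6.2 adds PTE eradication by pathogen and by MIC.

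**The concern.** PTE is meant to show that the infection stays cleared after study drug stops. EOT urine is taken on the last dosing day or within 2 days. PTE is on Day 21 ± 2, which is 9 to 16 days after a last dose on Days 10 to 7 (19 − 10 = 9; 23 − 7 = 16). A relapse and its rescue can fall inside that interval. The EOT culture may also be negative because drug is still in the urine. In the earlier cystitis study cited in protocol 7.4, mean Day 5 urine concentrations were 17 to 48 µg/mL, against an *E. coli* MIC90 of 2 µg/mL. Those are on-treatment values, so this is plausible but not shown.

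If the rescue drug then sterilizes the Day 21 urine, the rule credits study drug. That raises PTE eradication rates, may blur the by-pathogen and by-MIC tables, and matters because SAP Section 9 says the study is to inform dose selection for a possible Phase 3 program.

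**Working it through.** **1. Follow one subject through the rules.** Assume a negative EOT culture, relapse and rescue for pyelonephritis on Day 14, and sterile urine on Day 21.

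| Rule | Result |
|---|---|
| SAP Table 7, PTE | Eradication (no EOT persistence to carry forward) |
| SAP Table 8, PTE | Microbiologic success |
| Protocol 7.14 and 8.8.1.2 | Clinical failure |
| Protocol 12.5.1 composite | Overall failure |
| SAP 4.4 item 3b | Kept in CE-PTE, so can enter ME-PTE |

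The indeterminate category does not catch her. SAP 4.5 treats a culture as interpretable when the baseline pathogen can be excluded; what makes a culture uninterpretable there is growth of more than two isolates. SAP Appendix 4 imputes unknown antibacterial dates through PTE, but no visible microbiologic rule uses those dates.

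**2. The plan's own figures.** The documents give no figure for microbiologic response or rescue. The nearest are the composite power figures in SAP 3.1: 65% and 68% at N = 30 for success rates 0.69 and 0.78, and 80% at N = 80 and N = 64. Exact binomial enumeration, with Beta(0.5, 0.5) priors and the one-sided criterion P(difference > −0.10) ≥ 0.70, gives 66.2%, 68.1%, 80.5% and 80.8%. These agree to within 2 points. They do not bear on the rule itself. They confirm the scale: 150 micro-ITT subjects over 5 arms is 30 per arm, so one subject is 1/30 = 3.3 points.

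**3. Size of the inflation.** Let e be the share with EOT persistence, r the share failing only after a negative EOT culture, f the share of r rescued before the PTE culture, and c the share of those cleared.

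- True sustained eradication = 1 − e − r
- Rate under the rule = 1 − e − r + r·f·c
- Inflation = r·f·c, never negative

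All values below are assumptions: true rates 80% (levofloxacin, L) and 65% (an omadacycline arm, O), a true difference of −15 points, and c = 0.9. For example, with r = 0.15 and 0.30 and f = 0.5: L = 0.80 + 0.15 × 0.5 × 0.9 = 0.8675; O = 0.65 + 0.30 × 0.5 × 0.9 = 0.785. Percentages are unrounded.

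| Scenario (e and r as L / O) | f | L % | O % | Difference |
|---|---|---|---|---|
| Arms differ only after EOT (e 5/5, r 15/30) | 25% | 83.375 | 71.750 | −11.625 |
| Same | 50% | 86.750 | 78.500 | −8.250 |
| Same | 75% | 90.125 | 85.250 | −4.875 |
| Mixed (e 5/12.5, r 15/22.5) | 50% | 86.750 | 75.125 | −11.625 |
| Arms differ only in EOT persistence (e 5/20, r 15/15) | 50% | 86.750 | 71.750 | −15.000 |
| Rescue more complete in the stronger arm (e 5/5, r 15/30) | L 75%, O 25% | 90.125 | 71.750 | −18.375 |

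With equal f and c, the part of the difference that arises after EOT is multiplied by (1 − f·c). The part due to EOT persistence is unchanged.

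**The case against.** **The composite is not inflated by rescue.** A reader might infer that it is. It is not: rescue for pyelonephritis is a clinical failure, and so a composite failure. The composite is exposed only when an active drug is given for another reason to a clinical success, for example for a distinct new infection, which protocol 8.17.5 has recorded as an adverse event. Such subjects are already outside CE-PTE and ME-PTE, so this concerns micro-ITT only.

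**The direction is not fixed.** It is tempting to say that differences between arms shrink. The last two rows of the table show that they need not, and the documents give no relapse, rescue or clearance rates.

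**The documents do not disagree about antibacterials between EOT and PTE.** Exclusion 3 ("Anticipated need for systemic antibacterial therapy other than test article (for treatment or prophylaxis) during the study period") concerns need foreseen at entry. Protocol 7.13 ("All of the following therapies are excluded starting from the time of consent through EOT visit") sets a prohibition period. SAP 4.4 defines an evaluable population. Each can stand beside the others. Resumed prophylaxis is also a poor example, because exclusions 2 and 3 both address it.

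**Consequences are limited.** Efficacy endpoints are exploratory (SAP 7.1). The visible microbiologic analysis gives per-arm rates, offered in support of the clinical findings. The between-arm differences and posterior probabilities that can be read are those for clinical response (SAP 7.2.1).

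**A rule may exist elsewhere.** SAP 7.1.2.3, 7.1.3, 7.2.2.2, 7.2.2.3, 7.2.3 and 7.2.4.1 are in the contents list but their text is not in the public copy, and the Pathogen and CE Review Plan is a separate document. SAP 7.2.2.1 uses presumed eradication and presumed persistence, which the visible text does not define.

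**Culture-only scoring can be defended** as describing urine status whatever else was given. But SAP 5.3 states the opposite intent, and scoring rescue as failure would force agreement in the concordance table. That last point stands and shapes the fix.

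These points narrow the finding. They do not supply a rule in 7.1.2.2, and protocol 8.9, which is complete in the public text, has none.

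**Conclusion.** As visible, the rule counts a Day 21 culture cleared after rescue as eradication, and this departs from the intent stated in SAP 5.3. Inflation of PTE microbiologic success is certain whenever such a case occurs: r·f·c per arm, or 3.3 points per subject at 30 per arm. In the scenarios with arms differing only after EOT and f of 25% to 75%, it is 3.4 to 10.1 points in the arm with r = 15% and 6.8 to 20.3 points in the arm with r = 30%. It affects micro-ITT for any active antibacterial, and ME-PTE for rescued clinical failures only.

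Shrinkage of arm differences is a possibility. It requires more relapse after EOT on the weaker regimen, with similar rescue and clearance in both arms. This is worth correcting before unblinding, but it does not threaten the composite through rescue. The conclusion rests on the visible text; a rule in the unavailable sections or the review plan would reduce it to a missing cross-reference.

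**What to change.** 1. In SAP 7.1.2.2 (Tables 7 and 8), in line with SAP 5.3, state that a subject who receives, for the index infection and before the PTE culture, a systemic non-study antibacterial potentially active against the baseline pathogen is a microbiologic failure at PTE (presumed persistence), whatever that culture shows. Define presumed persistence there, since SAP 7.2.2.1 already uses it.
2. Keep the culture-only result as a sensitivity table, and use it for the clinical/microbiologic concordance table so that agreement is not built in.
3. For active antibacterials given for other reasons, add a micro-ITT sensitivity analysis that treats the PTE culture as indeterminate. Making this the main rule would be debatable, because a subject cured by study drug would no longer count as a success.
4. If such a rule already exists in another section or in the Pathogen and CE Review Plan, cite it in 7.1.2.2 instead.

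Cost: a few lines of SAP text and a programming flag. Protocol 7.12 and 8.18 already collect antibacterial dates, dose, route and reason. Reported microbiologic success falls by the share of subjects rescued and cleared, which could be several points in an arm if relapse after EOT is common.
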